1. AMENDMENT HISTORY

Amendment No.	Protocol Version No.	Date issued	Author(s) of changes	Details of Changes made
	3	1/11/17	[name] [name] [name]	
SA#02	4	1/04/18	[name] [name]	 Clarifications, Typos, Additional Author. Follow up duration extended to 6 months from 8-16 weeks. Inclusion Criteria (i) amended to say that all patients need to be able to give consent not just the acute patients The number of visits the Healthy Volunteers will have is 2 instead of 3. ACQ questionnaire in the table schedule was supposed to have been the AQLQ questionnaire, however this typo was missed at the last amendment. ACQ amended to AQLQ Added the NASA Task Load index. CRP & FBC blood tests have been removed from the pneumonia V1b visit. Quadriceps Ultrasound removed in Heart failure patients. 4 Meter Gait in Heart failure subjects removed from Visit V1a and added to. This test has been

Page 6 of 46

			completely removed from Healthy
			Volunteers.
		-	Physical exam removed from Visit 2
			in Healthy Volunteers.
		-	Review of AE & SAE at Visit 1a
			removed for Paediatric patients.
		-	Lung function clarification given that
			spirometry is both Pre and Post
			bronchodilator to match the patient
			information sheets.
		-	Removed the questionnaire from
			the appendix of the protocol.

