	Discovery Phase (years 1-2): Acute Heart failure (n=55-100), Community acquired pneumonia (n=55-100), adult exacerbations of asthma and COPD (n=110-200), paediatric exacerbations of acute childhoodwheeze and/or confirmed asthma (n=50-100), Age/Home environment matched Adult/Sibling/Parent/Spousal healthy volunteers (n=55-150 adults/50 children)
	Replication Phase (years 3-4): Acute Heart failure (n=55-100), Community acquired pneumonia (n=55-100), adult exacerbations of asthma and COPD (n=110-200), paediatric exacerbations of acute childhood wheeze and/or confirmed asthma (n=25-50), Age/Home environment matched Adult/Sibling/Parent/Spousal healthy volunteers (n=55-75 adult/25 children)
	Additional patients with stable COPD/Asthma/Heart failure n=200 Total Sample Size = 550-1250 patients.
Follow-up duration	Acute care participants will have up to 2 visits whilst an inpatient followed by a 'Post-Acute Event Recovery' at a minimum of 6 weeks post discharge and up to 6 months. Stable state participants and healthy volunteers will have 2 visits over 16 weeks. All participants will have outcome data 2 years post recruitment.
Planned Trial Period	3 years
Primary Objective	To evaluate the sensitivity, specificity, positive and negative predictive value of metabolomic biomarkers in exhaled breath samples to identify acute breathlessness, defined as one or more of (i) patient defined acute breathlessness and/or a (ii) 1 unit increase in Extended Medical Research Council breathlessness score (eMRC).
Secondary Objectives	To replicate selected metabolomic breath biomarker panels of acute breathlessness using a combination of both (i) discovery technologies (including GC-MS) and (ii) point of care auto tuned breath sensing devices (including linear IMS, CMS, PTR-MS).
	2) To evaluate the primary endpoint stratified by breathlessness as follows (i) change in eMRC by 1 unit, (ii) patient defined breathlessness and (iii) 100 mm visual analogue score for breathlessness
	To discover and replicate metabolomic breath biomarkers that differentiate (i) Acute Heart failure, (ii) Community acquired pneumonia, (iii) Adult exacerbations of asthma and COPD

	To quantify the level of clinical uncertainty in the primary diagnosis using a 100 mm visual analogue scale and independent clinical adjudication of case notes blinded to the following blood biomarkers (i) CRP (ii) blood eosinophils (iii) BNP (iv) Troponin-I but not clinical history and chest X-ray.

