A standard definition for acute breathlessness does not exist. We will use the presence of patient reported acute breathlessness, above their usual baseline breathlessness (i.e. in stable state) as a binary variable. We will also use the extended MRC score, and 100mm visual analogue score (VAS), as a continuous variable.

The extended MRC score has been validated in chronic disease populations, including in the acute state, and may be applied to diseases other than COPD where originaly validated. We will define a change in breathlessness of the eMRC as at least a unit change from stable state. In addition a VAS score will be used to measure breathlessness.

Definition of Post Exacerbation Recovery

Patient recovery will be defined as

- (i) Patient reported recovery from the acute exacerbation spell and back to their baseline extended MRC score or clinician defined recovery from the acute exacerbation spell and
- (ii) At least 6 weeks post exacerbation event (up to 6 months).
 - 6.2 Summary of Additional Assessment and breath sampling procedures/ devices

A number of analytical devices will be utilised to sample breath in acutely ill patients and based upon the (i) clinical site, (ii) operational needs and likely patient grouping (severity of underlying condition at the point of admission) within each clinical site, (iii) balance of discovery and point of care sensing technologies: breath sensors will be co-located to the two EMBER acute admissions units. All devices will be maintained to a high level of operational readiness by the technicians and device specialists within the clinical operations group. All devices will be checked for safety by Medical Physics at University Hospitals of Leicester NHS Trust.

[figure not shown]
The following devices will be utilised to evaluate breath volatile organic compounds

Page 18 of 46

- A portable mass spectroscopy device (Advion Ltd) for discovery based metabolomic breath sampling. This device is also capable of real time sampling.
- A proton transfer mass spectroscopy device (PTRMS) for discovery based metabolomic breath sampling.
- A point of care GC-FAIMS Lonestar device (Owlstone Nanotech Ltd)
- A point of care linear IMS Bioscout device (Owlstone Ltd: GC-FAIMS Lonestar analyser)

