- For acute admission the study team will approach the spouse, parent or sibling of the index case and seek informed consent for study assessments. All healthy subjects will undergo at last two assessments seperated by a duration of up to 6 months to match the acute (visit 1a) and stable state (visit 2) time period elapsed in their index case partner/spouse/sibling/child.
- Additional healthy volunteers will be identified from local recruitment databases and via advertising

Additional patients with chronic asthma, COPD and heart failure (trial participants group (vi) – see synopsis) will be identified via cardiology and respiratory outpatient clinics at Glenfield Hospital, paediatric respiratory outpatient clinics at the Leicester Royal Infirmary, from NIHR Leicester Biomedical Research Centre (BRC) patient research databases and will undergo up to 2 visits over a 6 months period. In all cases permission for recruitment from outpatients will be sought from the responsible consultant for the patient. The rationale for inclusion of this population is to have a stabe state disease control population that have been characterised over the same overall reporting period (stable state for measurements and 2 years for outcome data collection) as the acute population.

Analysis platform

Admissions
coding
(HISS/DW)

Demographics
(PMI)

Pathology
(ILAB/DW)

PFTS
(Expair)

UHL data sources

KEY

UHL data source

EMBER CP component

Figure 5: Clinical informatics organogram

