For the secondary analysis pertaining to other definitions of acute breathlessness, visual analogue breathlessness scores (100mm) and a 1 unit increase in the extended medical research council analysis outlined above for the primary endpoint will be performed based upon stratification of breathlessness type.

For the secondary analyses pertaining to discovery of breath metabolomics markers the outcome is a nominal variable with levels (1) Acute Heart failure (2) Community acquired pneumonia 3) Adult exacerbations of asthma/COPD (both in combination and considered individually) and (4) Acute exacerbations childhood wheeze and confirmed asthma in children. The relationship between the primary outcome and the metabolomics biomarkers in exhaled breath sample will be modelled using multinomial logistic regression and ROC curves. In addition to metabolomics markers the following independent variables will be included in the models where necessary (improve model fit): age, sex, validated co morbidity scores such as the Charlson score, indicator disease risk scores such as the CURB-65 pneumonia score, DECAF COPD exacerbation scores and treatments commonly used acutely for the indicator diagnoses.

Subsidiary Analysis

For subsidiary analyses modelling risk of re admission, death and length of stay we will utilise the following approaches

- Cox proportional hazards model will be fitted and competing risk models will be fitted for readmission. Logistic regression analysis will be used when looking at risk at particular time points for readmission.
- The number of exacerbation events will be modelled using Poisson or Negative Binomial regression.
- Relationship between death and breath biomarkers will be evaluated using a logistic regression model.

Page 33 of 46

For subsidiary analyses pertaining to dynamic profile of breath biomarkers during (i) the acute states (time points 1a), (ii) transition to the stable state (time point 1b) and (iii) in the chronic state 8-12 weeks post exacerbation (time point 2), a repeated measures model with a random intercept and random effect for time will be fitted, the random effects will be fitted for each patient. For the repeated measures mixed model an unstructured covariance will be assumed.

Other outcomes are exploratory and based around feasibility of an acute care platform for airways disease. Statistical analyses for these outcomes will be performed as appropriate for hypotheses derived in this exploration.

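### Section 10.1 places time point 2 at 8-12 weeks while the visit schedule allows 6 weeks to 6 months, and the control interval is 16 weeks in one place and up to 6 months in another

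*Protocol*

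**What the plan says.** **Acute patients.** In the protocol, section 10.1 (Subsidiary Analysis) models breath biomarkers over three points: the acute state (1a), the transition (1b), and a last point described as "in the chronic state 8-12 weeks post exacerbation (time point 2"). The model has a random intercept and a random time effect for each patient. Section 6.1, under the definition of recovery, sets the timing at "At least 6 weeks post exacerbation event (up to 6 months"). The synopsis places the recovery visit "at a minimum of 6 weeks post discharge and up to 6 months". The range is the same in these last two places, but the clock starts at the event in one and at discharge in the other.

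**Controls.** The synopsis states: "Stable state participants and healthy volunteers will have 2 visits over 16 weeks". Section 8.2 has healthy subjects undergo "two assessments seperated by a duration of up to 6 months to match the acute (visit 1a) and stable state (visit 2) time period" that elapsed in their index case. It says that stable-disease participants "will undergo up to 2 visits over a 6 months period", with no index case involved.

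**Analysis set.** Section 10.7 includes everyone eligible who consented and took part in either phase. It sets no condition on visit timing.

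**The concern.** A timing definition in the analysis section disagrees with the schedule that generates the data. An analyst following section 10.1 cannot tell whether a sample taken at 7 weeks or at 20 weeks belongs to time point 2, or whether time in the model means nominal visit or elapsed time. One reading leaves out visits that the schedule permits. The other reports samples taken anywhere from 6 to 26 weeks as a single 8-12 week state.

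Timing is also unlikely to be unrelated to clinical course. Section 6.1 requires recovery to be reported by the patient or judged by the clinician, so slow recoverers come later. It also resets visit 2 after a readmission that occurs before visit 2. A patient readmitted at week 7 could not satisfy a 6-week minimum until at least 7 + 6 = 13 weeks after the first event, already past the 8-12 week band on the first clock. Section 9.1.5 expects COPD readmission of 20% at one month and 33% at three months, so such cases are foreseeable.

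The control discrepancy is a separate matter. It bears on whether healthy volunteers can be sampled over the same interval as their index cases.

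**Working it through.** The plan gives no figure of its own to reproduce, so the check is interval arithmetic followed by a sensitivity range.

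**Inputs**
- Time point 2 in the model: 8 to 12 weeks (section 10.1).
- Permitted visit 2: 6 weeks to 6 months (synopsis; section 6.1). Six months is taken as 24 to 26 weeks.
- Control follow-up: 16 weeks (synopsis) against up to 6 months (section 8.2).

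**Step 1: share of the permitted window inside 8-12 weeks.** Share = (12 - 8) / (upper limit - 6).
- Upper limit 26 weeks: 4 / 20 = 20% inside, 80% outside.
- Upper limit 24 weeks: 4 / 18 = 22% inside, 78% outside.

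**Step 2: effect of the time origin.** If the window runs from discharge and discharge falls L weeks after the event, the permitted range on the event clock is 6 + L to 26 + L. It is still 20 weeks wide. The 8-12 week band stays wholly inside it as long as 6 + L is at most 8, that is, L of 2 weeks or less, and the 20% is then unchanged. For longer stays less of the band is reachable.

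**Step 3: from calendar time to samples.** The documents give no distribution of visit times. Under assumed distributions truncated to 6-26 weeks, the share of visits inside 8-12 weeks is:
- uniform: 20%;
- exponential delay after week 6, mean 2 to 10 weeks: 31-39%;
- normal, mean 10 and SD 2: 70%; mean 10 and SD 3: 54%;
- normal, mean 8 and SD 2: 57%;
- normal, mean 12 and SD 4: 37%;
- normal, mean 16 and SD 5: 16%.

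Across these cases the share of samples outside runs from about 30% to 84%. The 78-80% is therefore a statement about calendar time only.

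**Step 4: control interval.** Share of the patient window later than 16 weeks = (upper limit - 16) / (upper limit - 6).
- Upper limit 26 weeks: 10 / 20 = 50%.
- Upper limit 24 weeks: 8 / 18 = 44%.

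This treats the patient's clock and the control's clock as starting together. Section 8.2 counts from visit 1a, so the figure is approximate.

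**The case against.** The best defence is that 8-12 weeks is only a descriptive label. Section 10.1 states no exclusion by timing, section 10.7 takes all eligible participants, and section 6.1 carries the operative recovery definition. Detailed methods are referred to a separate data analysis plan that is not at hand, so silence on nominal versus elapsed time is not in itself a fault. The analysis is subsidiary and serves an exploratory aim. The primary analysis uses recovery as an outcome level but cites no 8-12 week window.

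Much of this stands, and it rules out several stronger readings that a reader might infer:

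- *Most visit-2 samples fall outside the window.* Not shown. With visits clustered near week 10, most would fall inside.
- *Valid samples will be dropped, or treated as missing and imputed under section 10.5.* No passage says so. It is one possible reading of an ambiguous label.
- *The protocol gives three windows for one time point.* The 16 weeks belongs to healthy and stable participants, whom section 10.1 does not place in the dynamic-profile model. There are two separate discrepancies.
- *Stable participants are matched to an index case.* Section 8.2 says this of healthy subjects only.
- *Season or instrument drift biases the dynamic-profile result through the controls.* The model describes change within patients, and section 6.1 accepts that healthy volunteers may be sampled at different times from patients. Drift is conceivable in patient-control comparisons, but the documents do not establish it.

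What the defence does not remove is the contradiction. The protocol prints a specific interval in its analysis section that disagrees with its own schedule, and it prints two intervals for controls. The amendment history, which records "Follow up duration extended to 6 months from 8-16 weeks", may explain how this arose. The finding does not rest on it, since both conflicts lie within the current text.

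**Conclusion.** The point holds as two timing contradictions in the current protocol.

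1. For acute patients, section 10.1 describes time point 2 as 8-12 weeks, while the synopsis and section 6.1 allow 6 weeks to 6 months from different origins. About 78-80% of the permitted calendar window lies outside 8-12 weeks, taking 6 months as 24 to 26 weeks. The share of samples affected is unknown.
2. For controls, the synopsis and section 8.2 disagree, 16 weeks against up to 6 months. A 16-week limit cannot deliver the stated matching of healthy subjects to patients who return after week 16, which is 44-50% of the permitted window.

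The established consequence is that time point 2 is undefined or mislabelled in the dynamic-profile analysis, and that the intended control interval is unclear. It should be corrected, but the stakes are modest: the model is subsidiary, and neither the sample size nor the stated primary analysis depends on the 8-12 week figure.

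**What to change.** - Reconcile the synopsis, section 6.1 and section 10.1 to one visit-2 window and one time origin. State which admission starts the clock for a patient readmitted before visit 2. Which window is intended is for the investigators to decide.
- In section 10.1, replace the 8-12 week label with that window, and use elapsed time since the acute event as the time variable, so that early and late recovery samples are not treated as simultaneous.
- Reconcile the control interval between the synopsis and section 8.2, stated separately for healthy subjects (with the matching aim) and for stable participants.
- Derive elapsed days before export. Section 14 de-identifies clinical data by, among other steps, deleting or moving dates. Table 1 lists admission and discharge timing but has no explicit row for visit date, so confirm that visit dates are captured.

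The cost is protocol wording plus one derived variable. No added visits, samples or participants follow from it.

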10.2 The Number of Participants

The sample size for the study is based on the requirements of the multinomial logistic regression model for the primary analysis. We estimate that if the number of events to number of variables in the model is in the ratio 20:1 a sufficiently large sample size will be obtained [24]. We regard this study as being exploratory it will serve as a basis for determining the sample size required for a larger study in the future. (Appendix D)

- 10.3 The Level of Statistical Significance
- All tests will be performed at the 5% significance level.
- 10.4 Criteria for the Termination of the Trial. Last participant, last visit
 - 10.5 Procedure for Accounting for Missing, Unused, and Spurious Data. Describe

A table listing all key variables with percentage of missing data will be reported and where possible the reason for missing data will be reported. Missing data will be imputed using PROC MI in SAS. Spurious data will be reported and where possible correct values will be inserted, if it is not possible to supply correct values value will be deleted.

10.6 Procedures for Reporting any Deviation(s) from the Original Statistical Plan An interim sample size calculation will be performed at the end of the discovery phase (Quarter 2, year 3) of the project; this calculation will identify the optimal number of patients in each replication phase disease indicator group based upon the optimal number of metabolomic biomarkers associated with the disease and the key outcome data from the discovery phase e.g. risk prediction, 30 / 60 day re admissions, discrimination of disease state from healthy state.

10.7 Inclusion in Analysis

All eligible participants, that have provided informed consent and participated in either discovery or replication phase studies.

11.DIRECT ACCESS TO SOURCE DATA/DOCUMENTS

Direct access will be granted to authorised representatives from the sponsor, host institution and the regulatory authorities to permit trial-related monitoring, audits and inspections.

12. QUALITY CONTROL AND QUALITY ASSURANCE PROCEDURES

The study will be conducted in accordance with the current approved protocol, ICH GCP, relevant regulations and standard operating procedures.

Page 34 of 46

Internal monitoring by the research team within the BRC will be performed according to ICH GCP. Data will be evaluated for compliance with the protocol and accuracy in relation to source documents. Following written standard operating procedures, we will verify that the clinical study is conducted and data are generated, documented and reported in compliance with the protocol, GCP and the applicable regulatory requirements.

The EMBER clinical operations group and clinical work stream group (WP4) described in section 15 of this protocol will meet fortnightly and monthly respectively to discuss overall quality control and assurance of the clinical study. In addition the University of Leicester operates a risk based audit programme to which this study will be subject to.

13. CODES OF PRACTICE AND REGULATIONS

13.1 Ethics

The study will obtain ethical approval from an approved ethics committee and be registered on a trial database.

13.2 Sponsor Standard Operating Procedures

All relevant Sponsor SOPs will be followed to ensure that this study complies with all relevant legislation and guidelines

13.3 Declaration of Helsinki

The Investigator will ensure that this study is conducted in full conformity with the current revision of the Declaration of Helsinki (last amended October 2000, with additional footnotes added 2002 and 2004).

13.4 ICH Guidelines for Good Clinical Practice

The Investigator will ensure that this study is conducted in full conformity with relevant regulations and with the ICH Guidelines for Good Clinical Practice (CPMP/ICH/135/95) July 1996.

13.5 Approvals

Once Sponsor authorisation has been confirmed, the protocol, informed consent form, participant information sheet and any proposed advertising material will be submitted to an appropriate Research Ethics Committee (REC) and host institution(s) for written approval.

Once Sponsor authorisation has been confirmed, the Investigator will submit and, where necessary, obtain approval from the above parties for all substantial amendments to the original approved documents.

13.6 Participant Confidentiality

The trial staff will ensure that the participants' anonymity is maintained. The participants will be identified only by initials and a participants ID number on the CRF and any electronic database. All documents will be stored securely and only accessible by trial staff and authorised personnel. The study will comply with the Data Protection Act which requires data to be anonymised as soon as it is practical to do so.

13.7 Other Ethical Considerations

The key ethical consideration specific to the MRC-EMBER study is the recruitment of acutely unwell patients that may not be able to provide informed consent. A hierarchical consent process will be adopted for the study with gold standard always being written patient informed consent at time point 1a, whilst accepting that for some patients and children personal legal representatives may be required to give written infirmed consent pending patient consent. In all cases written consent from the patients or parent in the case of young children will be obtained prior to time point 1b assessments.

Page 35 of 46

